### 4.7 Recruitment

Because of the nature of the study, recruitment of patients will be automatic.

PACU providers will be determined from the schedule and approached in the morning of their shifts for consent for participation.

#### 4.8 Allocation

Allocation is determined solely by entry time into the study.

### 4.9 Blinding

Patients will not be directly informed of their involvement in ODIN-Pilot, nor are they likely to discover this as the intervention occurs while they are under or emerging from anesthesia. Clinicians will be unblinded by the nature of the intervention; however, they will not know if a non-contact patient is included in the study.

### 5 Data collection, management, analysis

### **5.1 Data Collection Methods**

Pre- and intraoperative data will be extracted from the EHR and AlertWatch as specified in the TECTONICS (IRB# 201903026) protocol identically to the clinical operations of the ACT. Postoperative exploratory outcomes and patient demographics will be extracted from the EHR by an Institute for Informatics data broker. Survey instruments are included in the appendix and above. Because of the nature of study timing and extraction of data collected during the normal clinical process, no additional retention efforts of patient-level communication is planned.

### **5.2 Data Management**

Preoperative and intraoperative data used for machine learning will not be retained for this study, but other studies and clinical operations may share the same hardware. Only the minimum necessary private patient information will be collected for the purposes of the study. Any protected health data will be kept in a secure digital environment that is password protected and limited to research team only as discussed above. De-identified data may be kept and used in future studies not pre-specified in the above protocol. The investigators are responsible for ensuring the accuracy, completeness, legibility, and timeliness of the data collected. Data storage and safety practices are discussed above. Surveys of postoperative providers will be stored on REDCap.

The ACT will use clinical applications available to all clinicians to monitor ongoing surgical procedures. These applications can only be accessed over the secure hospital network or by VPN. This arrangement meets and/or exceeds HIPAA standards Patient Health Information (PHI) security. AlertWatch® is an approved clinical application at Barnes-Jewish Hospital, and therefore maintains these same levels of protection. Access to the data collected in this study will be restricted to approved personnel. It is a strict policy that PHI content cannot be reviewed outside of this protected environment. When possible, extracts from this project will avoid the use of PHI. De-identified patients can be identified using a special, non-PHI primary key which will be stored on the RIS Data Storage Platform.

Data will be maintained for at least seven years after the close of the study in accordance with Washington University guidelines. Further study record retention will be at the discretion of the study investigator. Data may be used for future studies not mentioned in the protocol.

#### **5.3 Statistical Methods**

Differences in the rate of acceptable handoffs will be compared with chi-square contingency table tests.

Although the primary analysis is intention to treat (comparing the with- and without-intervention groups directly), we will report as exploratory analyses per-protocol analyses in which patients whose report card was never accessed (outside of the ACT) are excluded.

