For each included patient, the ACT clinician will review the report card information, and the postoperative providers will receive it via a print-out or an Epic Best Practices Advisory integrated into their workflow. Our study will include 3 phases: (1) pre-intervention observation of handoff practices, (2) education and workflow adaptation of the intervention, and (3) non-randomized evaluation. During the education and non-randomized evaluation phases, some days will be without-intervention and others with-intervention. On with-intervention days, all eligible patients on a given day will receive the intervention. On without-intervention days no patients will receive the intervention, but handoff outcome measures will be assessed. The main comparison will be between with-intervention and without-intervention days in the evaluation phase. The primary outcome measure we will study is handoff effectiveness in the recovery room or wards. We will also survey providers on any inaccurate items, or major omissions.

This study will be conducted with a waiver of informed consent. It offers non-significant risk to patients. The ML report card will not recommend specific treatments, and decisions will remain in the hands of the supervising physician in all phases of care. The postoperative provider will also be given information about the report card and its limitations.

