However, the core ACT clinical protocol does not contemplate providing the data summary and ML-prediction information to the receiving provider in the PACU or surgical wards. The proposed Outcome predictions, Data summaries, and Interpretive Notes Report (ODIN-Pilot) study will provide a "report card" containing automatically generated summaries of pre- and intraoperative data along with ML output. This information will be presented to multiple postoperative providers with different contexts and use cases. PACU physicians and registered nurses (RNs) receive handoff from the intraoperative team and assume care for the patient in the immediate postoperative phase (typically 45 minutes to several hours). They observe for appropriate recovery from anesthesia, surveil for developing complications, treat common side effects of anesthesia. When the patient is ready to leave the PACU and communicate their findings to the wards (surgical inpatient unit) RN. The PACU team also communicates to the intraoperative surgical team, who communicates to the wards "midlevel" (advanced practice nurse or resident MD) responsible for routine medical oversight, modifying medication strategies, and ordering additional diagnostic studies if necessary.

We hypothesize several mechanisms by which this ML report card may improve patient outcomes. First, the report card will function as an "alert" for patients at high risk and direct attention to them. This additional review may reduce postoperative complications. Second, the report card may frame handoff communications around important data and issues relevant to the patient. By focusing the postoperative provider on potential problems, it may improve anticipatory guidance between the intraoperative, supervisory, and frontline team members.

This pilot study will not focus on patient outcomes, but will attempt to measure these potential mechanisms. We will survey postoperative providers to measure perceived handoff quality and coverage of important topics. We will validate these surveys with direct observations, debriefing interviews, and structured handoff evaluation tools.

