### 4.2 Participants and Eligibility

#### 4.2.1 Inclusion criteria

• Adults undergoing OR procedures in BJH South campus, including all of "Pod 2", "Pod

- 3", "Pod 5" and excluding all procedure suites such as Interventional Radiology, Parkview Tower "Pod 1", Center for Advanced Medicine "Pod 4", Labor and Delivery suites.
- Surgical service is "Acute and Critical Care Surgery", Otolaryngology, Hepato-biliary, Vascular, or Abdominal Transplant
- Planned non-ICU disposition ("floor" and "observation unit" collectively "ward" patients).
- Calculated risk of unplanned ICU admission in the first 7 postoperative days in the top 15% of historical records.

Risk of unplanned ICU admission will use the same calculator currently employed in the ACT. Risk factors considered include the surgery performed, demographics, laboratory values, comorbidities, vital signs, and medications.

Although patients are exposed to effects of the intervention, data is obtained from healthcare providers. Included providers are PACU nurses, PACU anesthesiology physicians, wards nurses, and wards midlevel providers (resident physicians, physician assistants, and advanced practice nurses) who are involved in a postoperative handoff for these patients.

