### 4.2.2 Durations and sample sizes

The planned duration and size of each phase is

- Pre-intervention observation: 60 working days, 50 patients
- Education and intervention delivery testing: 30 working days, 50 patients
- Intervention evaluation: 90 working days, 350 patients divided into 30 without-intervention days and 60 with intervention days.

The exact number of providers surveyed is difficult to project, because some providers will care for multiple patients, nurses and midlevel providers change their assignments, and staff turnover may occur. We anticipate surveying fewer than 60 distinct PACU RNs, fewer than 15 PACU residents, fewer than 20 PACU physicians, fewer than 60 distinct floor RNs, and fewer than 25 distinct midlevel providers.

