### 4.2.3 Case screening and identification

Patients eligibility is pre-screened automatically, and a researcher or ACT clinician verifies their eligibility. The first two enrollment criteria

- Adults undergoing OR procedures in BJH South campus, including all of "Pod 2", "Pod 3", "Pod 5" and excluding all procedure suites such as Interventional Radiology, Parkview Tower "Pod 1", Center for Advanced Medicine "Pod 4", Labor and Delivery suites
- Surgical service is "Acute and Critical Care Surgery", Otolaryngology, Hepato-biliary Surgery, or Abdominal Transplant Surgery

are taken from the surgical schedule. The third enrollment criteria

- Planned non-IČU disposition ("floor" and "observation unit" collectively "ward" patients). is taken from (1) the procedure schedule request, (2) the anesthesiologist day-of-service anesthesia plan documentation, (3) a predictive model based on the scheduled surgery. Cases with > 75% likelihood of direct ICU admission or outpatient discharge are automatically excluded by the predictive model. The final criterion
  - Calculated risk of unplanned ICU admission in the first 7 postoperative days in the top 10% of historical records.

is calculated using the same model described in 4.3.2

[figure not shown]
Once the server has identified patients as likely eligible, they are marked for review in the ACT

ML dashboard, where final eligibility is confirmed.

During the intervention evaluation (phase 3), each day will be with or without intervention for all eligible patients. These will rotate 2:1 over work days, eg week 1 = (with, with, without, with, with), week 2 = (without, with, with, without, with), week 3 = (with, without, with, without)

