#### 4.4 Outcomes

# **4.4.1 Primary Outcome Measures**

The primary outcome will be self-reported handoff effectiveness.

The following survey questions will be asked of postoperative providers:

Did you receive at handoff all the information you needed to safely take care of this patient?

[Yes, No]

Did you receive information from the team giving handoff to explicitly help you manage any potential complications or problems? [Yes, No]

If so, please list what problems / topics were discussed? [Free response]

[If with-intervention phase \* ] Did you look at or discuss the postoperative report card for this patient? [Yes, No]

[If  $^*$  yes] Did the report card contain any information that was notably misleading or incorrect?

[Yes, No]

[If yes, please describe: text box]

[If \* yes] Are there any important pieces of information that the computer should have included in the report card but didn't?

[Yes, No]

[If yes, please describe: text box]

[If \* yes] How much did the ML report change questions asked or information transfer at handoff?

[ Not applicable , Not at all , a little , a fair amount , a great amount ]

[If \* yes] How much effort was accessing the report card? [Very easy, easy, some effort, hard, unable to get to it or had to ask for help]

[If \* yes] Was the information presentation in the report card easy to understand? [Easy, some effort, hard to understand, unable to use or had to ask for help]

[If \* yes] Was the information in the report card relevant?
[a great amount, a fair amount, modestly, mostly not, not at all, not sure]

[If \* yes] Was the information in the report card useful to decision making or helpful to your understanding of the patient?
[a great amount, a fair amount, modestly, mostly not, not at all, not sure]

The following questions will additionally be asked of PACU resident physicians:

Did you participate in handoff for this patient? [Yes, No]

Did you visit this patient's bedside or speak to their nurse before being asked to sign them out? [Yes, No]

Figure 7 illustrates the RedCAP survey for safety questions which will be included throughout the study.

Figure 7: RedCAP Safety Survey

Postoperative Al Risk Report Card	Resize font:  Returning?

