### 4.4.2 Secondary Outcome Measures

A research assistant will directly observe up to 150 OR - PACU and PACU-Ward handoffs in the intervention phase. An assessment form is attached. After direct observation, the research assistant may ask unstructured clarifying questions and present the survey questions discussed above.

We will conduct 20-30 debriefing interviews with ward and PACU clinicians on their perception of handoff effectiveness and the usefulness of the report card. These will be audio recorded and transcribed.

We will extract exploratory clinical outcomes from the EHR: ICU admission, hospital length of stay, discharge disposition (including death), and changes in serum creatinine (acute kidney injury).

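### The primary chi-square treats handoff ratings as independent, although the arm is set by whole day, several roles can rate one patient, and no unit of analysis or rule for combining ratings is given

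*Combined protocol and SAP*

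**What the plan says.** **Test.** Section 5.3 states: "Differences in the rate of acceptable handoffs will be compared with chi-square contingency table tests". The primary analysis compares the two groups directly. Neither 5.3 nor any other section mentions a cluster term, robust variance, random effect or day-level analysis.

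**Assignment.** The Non-Technical Summary says: "On with-intervention days, all eligible patients on a given day will receive the intervention". Section 4.2.3 repeats that "each day will be with or without intervention for all eligible patients", in a fixed 2:1 rotation. Section 4.2.2 plans "350 patients divided into 30 without-intervention days and 60 with intervention days".

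**Raters.** Section 4.2.1: "Included providers are PACU nurses, PACU anesthesiology physicians, wards nurses, and wards midlevel providers". Section 4.4.1 introduces the primary outcome with "The following survey questions will be asked of postoperative providers", without limiting it to one respondent per patient. Section 1 describes more than one route of information. "PACU physicians and registered nurses (RNs) receive handoff from the intraoperative team"; the PACU then passes findings to the ward nurse; and the ward midlevel hears from the surgical team. Section 4.4.2 mentions "up to 150 OR - PACU and PACU-Ward handoffs in the intervention phase", but that is direct observation, a secondary measure.

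**Unit.** Section 4.5 dichotomizes surveys but sizes the comparison in patients (50 and 100). Section 5.3 compares handoffs, then excludes patients in the per-protocol analysis.

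**The concern.** Patients treated on one day share the arm, the PACU oversight and whatever else makes that day good or bad for handoffs. Ratings of one patient by different roles also share that patient's circumstances. If such ratings are positively correlated, the chi-square understates the variance, and the p-value for the primary objective (section 2.1) is too small.

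The undefined unit is the larger gap. If the PACU nurse answers yes and the ward nurse answers no for the same patient, the plan does not say whether that is one result or two, or which one counts. The denominator of the primary endpoint, and with it the degree of correlation, could be settled after the data are seen.

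**Working it through.** **1. The plan's own figures.** Section 4.5 gives an 18-point detectable increase from 70%, with 50 and 100 patients and 80% power. It states neither alpha nor sidedness. With pooled variance and independent observations, the detectable difference is 18.9 points at two-sided 5% and 17.2 one-sided. Power for 70% versus 88% is 75.3% two-sided. The other figure in 4.5, an upper limit of 2.4% for 0/150, reproduces (exact two-sided 2.43%). The gap between 18 and 18.9 is a separate sample-size point and is not used here.

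**2. Inputs.** From the documents: 30 and 60 days, 150 patients (4.5) or 350 (4.2.2), and 70% acceptable. Patients per day: 150/90 = 1.7 or 350/90 = 3.9. Assumed: latent-scale day ICC 0.05-0.10, added patient ICC 0.05-0.20, one to three ratings per patient, two-sided 5%.

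**3. Conversion to the observed scale at 70%.** ρ = (Φ₂(z, z; r) − 0.49)/0.21 with z = Φ⁻¹(0.70). Latent 0.05 becomes 0.029, 0.10 becomes 0.058, and 0.30 becomes 0.182.

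**4. Closed form.** Take k ratings per patient, n₀ control patients spread at random over 30 days, ρd for two ratings on the same day, and ρs for two ratings of the same patient (day plus patient part):

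DE = 1 + (k − 1)ρs + k((n₀ − 1)/30)ρd; true error = 2(1 − Φ(1.96/√DE)).

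- One rating, 150 patients (n₀ = 50): 1 + (49/30)(0.029) = 1.047, error 5.5%; with 0.058, 1.095, error 6.1%.
- One rating, 350 patients (n₀ = 117): 1 + (116/30)(0.029) = 1.112, error 6.3%; with 0.058, 1.224, error 7.6%.
- Two ratings, 150 patients, day 0.05, patient 0.05: 1 + 0.058 + 2(49/30)(0.029) = 1.153, error 6.8%.
- Three ratings, 350 patients, day 0.10, patient 0.20: 1 + 2(0.182) + 3(116/30)(0.058) = 2.037, error 17.0%.

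**5. Simulation under the null** (20,000 runs per cell, with/with/without rotation, day effects independent between days):

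| Ratings pooled per patient | 150 patients | 350 patients |
|---|---|---|
| One | 5.5-6.3% | 6.2-7.6% |
| Two | 7.0-9.8% | 8.5-12.9% |
| Three | 8.1-12.4% | 10.3-17.4% |
| Four roles, 50% responding | 7.0-10.6% | 8.8-14.3% |

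With no day correlation the range over all these cases is 5.0-7.8%. A risk difference with day-clustered standard errors held 4.9-5.9% throughout. A second simulation with a wider observed-scale day ICC of 0.02-0.10 gave 6.1-10.2% for 350 patients with one rating each.

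**6. Dependence between days.** Adjacent days are often in opposite arms, so slow-moving effects largely cancel. For 350 patients, day ICC 0.10 and day autocorrelation 0.8, the chi-square error falls to about 5-6% for one rating and about 10-11% for three.

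**7. Shared raters.** A pool of 60 nurses working on both kinds of day gave 5.2-5.3%. If a single physician rated every patient of a day (an assumption), one rating per patient would give 5.6-6.7% (150) or 6.4-9.2% (350).

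**The case against.** The strongest reply is that the patient is the implied unit: 4.5 counts patients and the per-protocol sentence in 5.3 excludes patients. On that reading the clusters are small and numerous, and the excess error is minor. Much of this stands. Day clustering alone would be a modest defect. But an implied unit does not say which role's rating represents the patient, and the Non-Technical Summary places the primary outcome in both the recovery room and the wards.

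A second reply is that the error rates assume independent day effects. That also stands. The documents do not say how day effects behave, and the rotation protects against slow drift. Pooling several ratings still inflates error under every pattern tried.

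A third is that this is a pilot; section 4.5 says it mainly assesses perceived safety and workflow. That lowers the stakes. It does not remove the stated primary objective or the power claim made for it.

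A reader might infer that the plan intends to pool all surveys, or that the primary p-value is badly wrong whatever is done. The documents support neither: pooling is neither specified nor excluded, and one rating per patient gives only a small excess. A reader might also infer from section 4.3.1 that one physician rates every patient of a day. That section names an attending and a resident, and 4.3.3 has the resident phone change hands at each shift.

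**Conclusion.** The point holds and should be fixed. The textual part is certain: a test that assumes independence, assignment by day, up to four rating roles per patient, and no rule for combining ratings. The numerical part is conditional. Pooling two or three ratings per patient would put the true error of a nominal 5% test at about 7-12% with 150 patients or 8-17% with 350. One rating per patient gives about 5.5-6.3% or 6-8%. Every ICC and rating count is assumed, and independent day effects make these upper-end values. The undefined unit matters more than day clustering by itself.

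**What to change.** In section 5.3:

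1. State the unit of the primary analysis. Cover every surveyed role, including the ward midlevel, whose information comes through the surgical team and so fits neither OR-to-PACU nor PACU-to-ward. Say whether one prespecified role counts per patient or all ratings are kept.
2. Replace the chi-square with an analysis that accounts for calendar day, for example a risk difference or logistic GEE with day-clustered standard errors and a 95% interval. Clustering on day also covers same-patient correlation and needs no rater identity. The survey link carries patient and date (4.3.3). On days without a report card the date must still be known, because it determines the arm.

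In section 4.5, restate the detectable difference for the chosen test, with its alpha, sidedness and assumed day ICC. For orientation, with 50 and 100 patients, one rating each and two-sided 5%, a day-clustered test with unpooled variance detects about 20.0 points with no day correlation, and 20.4-20.8 at observed day ICC 0.03-0.06.

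The cost is SAP wording, a few lines of code and some power. At 50 and 100 patients and a true 18-point difference, power falls from about 76% to about 69-72% with no day correlation, depending on how the variance is estimated. At 350 patients and 13.2 points it is 80% against 76%. If neighbouring days are positively correlated, day-clustered standard errors will tend to be conservative under this rotation.

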### 3 Trial Design

The study will be a non-randomized experimental design with 3 phases. First, data about current practices will be collected before interventions begin. Second, we will pilot the mechanics of delivering the report card while educating users about it. Third, we will measure handoff and usability outcomes on alternating days with and without the intervention. (2:1 intervention to non-intervention). We anticipate the number of intervention-deliver and education days to be 30, but may have to periodically update the report card delivery requiring an additional delivery-testing period. During the entire study, we will accept and record any safety concerns from participants.

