ML output will be generated on a server controlled by the investigators and administered by Washington University Information Technology. This is the same server and data access mechanism used by the ACT team. A feed of preoperative and intraoperative data extracted from the Epic EHR designed for use in the AlertWatch system is currently saved in a database maintained by BJH and exposed for authorized users to access, which we will access using encrypted transport mechanisms. The server will also have a TLS-encrypted and password protected web interface (dashboard) for debugging, message generation, and manual end-ofcase triggering. The web interface will allow study technical staff and ACT clinicians to look up current and previous risk profiles by study identifier, patient identifier and date, or date, time, and operating room number. It will also allow them to manually enter that a case is concluding, and to mark a day as "with-intervention". The study identifiers, date, time, end of case marker, intervention indicator, and ML output will be stored on the WUSTL Research Infrastructure Services Data Storage Platform. The RIS Data Storage Platform is a scalable distributed storage solution with an integrated long-term archive. It is institutionally approved for protected health information, and requires WUSTL-key authentication and 2-factor authentication outside WUSTL facilities. Data access is granted only on a per-user basis and logged. The ML server is behind the Washington University firewall and inaccessible from off-campus computers.

To avoid misleading postoperative providers, we will create a brief educational sheet explaining the purpose of the study and the items included in the risk profile (attached). The educational sheet will include the calibration accuracy and other appropriate metrics regarding the predictions. For example, at the screening threshold we will use the sensitivity for AKI is about 50%, meaning that the provider should not be falsely reassured by not receiving an alert. We will stress that these risk predictions were formed in the context of usual care at BJH, and that a

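### The primary comparison of non-randomised days is an unadjusted chi-square, although predicted ICU risk and surgical service are determined at screening on both day types

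*Combined protocol and SAP*

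**What the plan says.** Section 5.3 gives the primary analysis in one sentence: "Differences in the rate of acceptable handoffs will be compared with chi-square contingency table tests". It calls this intention to treat, "comparing the with- and without-intervention groups directly". The only other analysis there is an exploratory per-protocol one that drops patients whose report card was never accessed. No covariate, stratum, regression or adjusted sensitivity analysis is named anywhere in the document.

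The design is stated openly in section 3: "The study will be a non-randomized experimental design with 3 phases". Section 4.8 adds: "Allocation is determined solely by entry time into the study". Section 4.2.3 describes the evaluation-phase days: "These will rotate 2:1 over work days".

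Two baseline characteristics are eligibility criteria in section 4.2.1. One is predicted risk: "Calculated risk of unplanned ICU admission in the first 7 postoperative days in the top 15% of historical records". The other is surgical service: Acute and Critical Care Surgery plus "Otolaryngology, Hepato-biliary, Vascular, or Abdominal Transplant". Under section 4.2.3 a day's type applies to all eligible patients, so both characteristics must be established on with-days and without-days alike.

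On storage, section 4.3.1 says that study identifiers, date, time, end-of-case marker, "intervention indicator, and ML output will be stored on the WUSTL Research Infrastructure Services Data Storage Platform". Service is not in that list. Section 4.2.3 says it is read from the surgical schedule. Section 5.2 says the raw inputs to the models are not retained; that does not cover the model output.

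**The concern.** Without randomisation, nothing in the design guarantees that with-days and without-days carry comparable patients. The rotation is predictable. Final eligibility is confirmed by a researcher or ACT clinician, and day type is marked in a web dashboard open to study technical staff and ACT clinicians (sections 4.2.3 and 4.3.1). No concealment from them is described. Section 4.3.4 also allows the screening threshold to move during the study.

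If patients on the two day types differ in predicted risk or service, and those characteristics relate to how a handoff is rated, the crude difference mixes that contrast with the effect of the report card. The test gives no way to see it. Correcting the standard errors for clustering would leave the same unadjusted estimate. Variation between services and risk levels also stays in the error term. At stake is the estimate for the primary objective in section 2.1.

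**Working it through.** **Inputs from the documents:** 70% acceptable at baseline, 50 v 100 patients, 18 points at 80% power (section 4.5); 350 evaluation-phase patients over 30 without-days and 60 with-days (section 4.2.2). At 2:1, 350 gives about 117 v 233.

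**Assumptions:** the documents relate neither risk nor service to handoff rating and give no service shares. Service shares, rating gaps and variance explained are therefore assumed. One independent response per patient is also assumed.

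1. **The plan's own figure.** With unpooled variance, SE = sqrt(0.70 x 0.30/50 + 0.88 x 0.12/100) = 0.0725. Power at one-sided 5% is Phi(0.18/0.0725 - 1.645) = 79.9%, so the 18 points reproduce on that basis. With a two-sided 5% pooled test, power at 18 points is 75.3% and the detectable difference is 18.9 points. Section 4.5 states neither alpha nor sidedness.

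2. **Detectable difference at the planned size.** The two-sided pooled calculation at 117 v 233 gives 13.2 points.

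3. **Chance imbalance in service.** SD = sqrt(p(1-p)(1/233 + 1/117)).
   - p = 0.20: 4.5 points.
   - p = 0.30: 5.2 points.
   - With a 20-point rating gap: 4.5 x 0.20 = 0.9 and 5.2 x 0.20 = 1.0 point (1 SD).

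4. **How that compares with the crude standard error.** At 70%, SE = sqrt(0.21 x (1/233 + 1/117)) = 5.2 points. The share of variance is (0.9/5.2)^2 = 3% to (1.0/5.2)^2 = 4%. The crude standard error already contains this component. Removing it narrows the interval by at most 1 - sqrt(0.96) = 2%.

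5. **Systematic imbalance, if it occurred.** Bias = imbalance x rating gap. Imbalances of 5 to 20 points with gaps of 10 to 30 points give 0.5 to 6.0 points. At 117 v 233, a 2-point bias (10 x 0.20) raises two-sided 5% type I error to 6.9%, and a 4-point bias (20 x 0.20) raises it to 12.8%.

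6. **Precision.** If adjustment explains a share R2 of outcome variance, effective sample size is n/(1 - R2). The detectable difference at 117 v 233 goes from 13.2 points to 12.9 (R2 = 5%), 12.6 (10%) or 12.0 (20%).

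7. **Can the data carry the model?** Day type (1), risk on the logit scale (1) and five services (4) make 6 parameters. At 70% v 88%, unacceptable handoffs number 0.30 x 117 + 0.12 x 233 = 35 + 28 = 63, or about 10 per parameter. At 50 v 100 they number 15 + 12 = 27, or 4.5 per parameter, so sparse services would need combining.

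8. **Weekday balance.** A strict with-with-without cycle over 90 working days in five-day weeks puts 6 without-days and 12 with-days on every weekday. The printed week 3 example has four days and breaks that cycle.

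**The case against.** The strongest reply is that little is wrong with a simple comparison here. Strict rotation balances weekdays, so the most obvious source of differing case mix is handled by design. Eligibility confines patients to a high-risk band. Step 4 shows that the service figure is sampling variation which the standard error already covers. No mechanism for systematic imbalance in service or risk is demonstrated. Section 4.5 describes the study as mainly about perceived safety and workflow. All of this stands as a limit on size. It does not justify leaving the primary estimate wholly unadjusted: section 2.1 makes the effect on handoff effectiveness the primary objective, section 4.5 gives that comparison a power statement, and the rotation neither conceals day type nor balances anything beyond the calendar.

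A second reply is that the model may be too large for the data. With risk and service only, about 63 events for 6 parameters is workable at the planned size. It would be tight at 50 v 100.

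A reader might infer three stronger things that the documents do not support.
- **That provider role should be a covariate.** The printed survey in section 4.4.1 branches only for PACU residents and has no general role item. Role is also fixed by who responds, after allocation. The survey link travels on the printout and the Epic advisory (section 4.3.3), while no report card is generated for without-day patients (section 4.3.5), so the intervention may itself affect who answers. A role term would not reliably repair that.
- **That every variable is already held at no cost.** Stored risk output is well supported. Retention of service is only implied.
- **That the crude result is known to be biased.** Nothing in the documents shows this.

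**Conclusion.** The point holds as a design-appropriate improvement of modest size. In a non-randomised comparison with predictable allocation, the plan ignores two baseline characteristics that it must determine for every eligible patient on both day types. The benefit is protection against imbalance plus a little precision: about 1 point at 1 SD of chance imbalance in service, and a detectable difference of 12.6 instead of 13.2 points. These figures rest on the assumed 20-30% service share, 20-point rating gap and 10% of variance explained, and on independent responses. Larger biases, up to 6 points, need a systematic imbalance that the documents do not demonstrate but also do not rule out. Naming the covariates in advance also prevents choosing them after the results are seen.

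**What to change.** In section 5.3, make the primary estimate a logistic regression of acceptable handoff on day type, adjusted for the preoperative (screening) predicted ICU risk on the logit scale and for surgical service. State in advance how sparse services are combined. Report a standardised risk difference with 95% CI, and keep the crude chi-square table as support.

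In section 4.3.1 or 5.2, state that screening risk and service are kept by study ID for without-day patients as well as with-day patients.

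Report results by provider role or handoff type only as a sensitivity analysis. If role is wanted, a non-identifying role question may have to be added to the survey.

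Sections 4.2.1 and 4.2.3 should be reconciled first, since they differ on the risk cut-off (top 15% v top 10%) and on whether vascular surgery is listed. Both bear on how the covariates are defined.

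The cost is a few sentences, up to five extra parameters, and possibly re-linking service from the surgical schedule. Clustering by day and provider, and differential survey response between day types, need their own provisions.
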